## List of abbreviations

---

AE	Adverse event
AMD	Age-related macular degeneration
BCVA	Best-corrected visual acuity
BRB	Blood retinal barrier
BRVO	Branch retinal vein occlusion
BSL	Baseline
BQA	Biostatistics Quality Assurance
CF	Color fundus photography
CMH	Cochran-Mantel-Haenszel
CRO	Contract Research Organization
CRVO	Central retinal vein occlusion
CSFT	Central subfield thickness
DAR	Drug administration record
DME	Diabetic macular edema
DS&E	Drug Safety and Epidemiology
eCRF	electronic Case Report Form
EDC	Electronic data capture
EOS	End of study
EOT	End of treatment
ETDRS	Early Treatment Diabetic Retinopathy Study
█	█
FAS	Full Analysis Set
IgG	Immunoglobulin G
IOP	Intraocular pressure
LOCF	Last observation carried forward
█	█
ME	Macular edema
MedDRA	Medical dictionary for regulatory activities
█	█
PFS	Prefilled syringes
PMDA	Pharmaceutical and Medical Devices Agency
PMS	Post marketing surveillance
PPS	Per Protocol Set
PRN	Pro re nata
█	█
RVO	Retinal vein occlusion
SAE	Serious adverse event
VA	Visual acuity
VEGF	Vascular endothelial growth factor
wAMD	wet age-related macular degeneration
WHO	World Health Organization

---

## Glossary of terms

Assessment	A procedure used to generate data required by the study.
Decimal VA	Visual acuity expressed as a decimal. Best-corrected visual acuity will be assessed in a sitting position using Decimal VA testing charts at an initial testing distance of 5 meters at every visit.
Screening	Point/time of patient entry into the study; the point at which informed consent must be obtained (i.e. prior to starting any of the procedures described in the protocol).
Enrollment	Point/time of patients to be randomized into the study; the point at which screening is completed and informed consent has been taken (prior to starting any of the procedures described in the protocol).
ETDRS (Early Treatment Diabetic Retinopathy Study)	A National Eye Institute-supported, multicenter, randomized clinical trial designed to evaluate photocoagulation and aspirin treatment in the management of patients with non-proliferative or early proliferative diabetic retinopathy.
Fellow treated eye	The fellow treated eye is the non-study eye treated with ranibizumab for visual impairment due to macular edema secondary to retinal vein occlusion.
Fellow untreated eye	The fellow eye that has not been treated with ranibizumab. The fellow untreated eye is the non-study eye until treated with ranibizumab for visual impairment due to macular edema secondary to retinal vein occlusion. After treatment, it becomes the fellow treated eye.
Investigational drug	The drug whose properties are being tested in the study; this definition is consistent with US CFR 21 Section 312.3 and is synonymous with "investigational new drug" or "investigational medicinal product."
Patient number	A number assigned to each patient who enrolls in the study. When combined with the center number, a unique identifier is created for each patient in the study.
Period	A minor subdivision of the study timeline; divides phases into smaller functional segments such as Screening, Baseline, titration, washout, etc.
Premature patient withdrawal	Point/time when the patient exits from the study before the planned completion of all study drug administration and assessments; at this time all study drug administration is discontinued and no further assessments are planned.
Randomization number	A unique identifier assigned to each randomized patient, corresponding to a specific treatment arm assignment.
Stop study participation	Point/time at which the patient came in for a final evaluation visit or when study/investigational treatment was discontinued whichever is later.
Study drug	Any drug administered to the patient or therapeutic procedure as part of the required study procedures; includes investigational drug and any control drugs or therapeutic procedure.

Study eye	The study eye is the eye selected by the investigator at Baseline (according to the protocol) to receive the study treatment.
Study treatment discontinuation	Point/time when patient permanently stops taking study treatment for any reason; may or may not also be the point/time of premature patient withdrawal.
Variable	Information used in the data analysis; derived directly or indirectly from data collected using specified assessments at specified time points.

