#### Inclusion criteria for study eye

3. Diagnosis of visual impairment exclusively due to ME secondary to BRVO.
4. BCVA score at Screening and Baseline (Day 1) between 0.5 and 0.05 decimal (i.e., between 73 and 19 letters in ETDRS testing) with Landolt C charts inclusively (i.e., approximate logarithm of the minimum angle of resolution (logMAR) units of 0.3 to 1.30).
5. At Baseline (Day1), a maximum BCVA gain of 0.2 units logMAR conversion inclusively from screening is allowed as long as the BCVA score does not exceed the upper limit of 0.3 units logMAR.
6. Increased central subfoveal thickness ( $> 300 \mu\text{m}$  at Baseline (Day 1) when measured by SD-OCT)
7. Duration of vision deterioration  $\leq 6$  months (determined by self-report) at screening.

If both eyes are eligible, the one with the worse VA at screening will be selected as study eye, unless, based on medical reasons, the investigator deems the other eye to be more appropriate for treatment and study.

If the fellow eye presents with visual impairment due to ME secondary to RVO, it may also be treated with ranibizumab medication, laser photocoagulation or others and in line with the Japanese label and at the discretion of the investigator, however, any anti-VEGF treatments other than ranibizumab is not allowed. The fellow eye treated with ranibizumab is then labeled the fellow treated eye. Bilateral treatment with ranibizumab cannot be performed on the same day. Bilateral treatment indicates the number of patients who received 3 or more injections of ranibizumab (study and fellow treated eye) within a  $30 \pm 7$  days period.

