## **Exclusion criteria for prior or current ocular treatment**

### **For both eyes**

23. Treatment (or anticipated treatment in the fellow eye for non-RVO indications during the study) with any anti-angiogenic drugs (including any anti-VEGF agents) within 3 months before Baseline (Day1) in fellow eye or before Baseline (Day 1) in the study eye (e.g., pegaptanib (Macugen®), ranibizumab (Lucentis®), bevacizumab (Avastin®), and aflibercept (EYLEA®)).

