#### **5.5.4.3 Treatment of the fellow eye**

Patients who develop visual impairment due to ME secondary to RVO in the fellow eye (non-study eye) during the study that, in the investigator's opinion, qualifies for and requires treatment, may be treated at the investigator's discretion according to the standard treatment, including administration of ranibizumab. Ranibizumab will be injected in accordance with the rule of usual care and should be applied as per Japanese label.

Treatments of the fellow eye with ranibizumab should not be performed on the same day as treatments with ranibizumab of the study eye. Treatment of the fellow eye must be scheduled in a way not to disturb the schedule for visits and treatments of the study eye. Treatment will be captured on the eCRF. The fellow treated eye must be monitored according to routine practice and AE(s) and serious adverse events (SAEs) are captured on eCRFs. If fellow eye is treated with ranibizumab, examinations will be same as study eye.

Treatment with other anti-VEGF medication (e.g., pegaptanib (Macugen®), bevacizumab (Avastin®), aflibercept (EYLEA®)) and intra- or periocular corticosteroids (including sub-Tenon) are prohibited.

Treatment with ranibizumab for non-RVO indications in the fellow eye will be permitted in the same rule with RVO in the fellow eye within the limits of Japanese package insert, but the other anti-VEGF medication is prohibited.

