### **9.3.2 Bilateral treatment**

The number of patients who received 3 or more injections of ranibizumab (study and fellow treated eye) within a  $30 \pm 7$  days period will also be summarized by treatment group within the Safety Set.

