### 9.5.2.1 Adverse events

Adverse events will be deemed treatment emergent if the onset date is on or after the date of first study treatment (Day 1). All treatment-emergent AEs will be summarized. Any AEs recorded prior to the start of study treatment will be listed separately and together with all other AEs.

Adverse events will be presented separately by site (non-ocular, study eye, fellow eye). Adverse events will be summarized by treatment group, presenting the number and percentage of patients having an AE in each primary system organ class and having each individual AE based on the preferred term. Patients who experienced multiple AEs for a preferred term will be counted once, similarly for patients with multiple AEs per system organ class.

All information pertaining to AEs noted during the study will be listed by patient, detailing AE (e.g., verbatim given by the investigator as well as the system organ class and preferred term according to MedDRA), date of starting and ending, causality, severity, relationship to the study drug or procedure, and eye (for ocular events). The AE onset will also be shown relative (in number of days) to the day of (first) initial study treatment (ranibizumab injection or laser photocoagulation as applicable) and relative (in number of days) to the Day 1.

Summary tables will also be presented and described for subsets of AEs, e.g. events potentially related to VEGF-inhibition. Adverse events which are part of the Risk Management plan (RMP) will be listed based on the latest RMP version available at the time of DBL.

The following AE listings will be provided:

- Any AE recorded before Day 1.
- Any treatment-emergent AEs with the exception of ocular AEs of the fellow untreated eye starting on or after first treatment with ranibizumab within this eye.
- Any treatment-emergent AEs of the fellow treated eye starting on or after the first treatment with ranibizumab within this eye.
- Any AEs for patients who (bilateral patients) received 3 or more injections of study drug within a  $30 \pm 7$  days period starting on or after the third injection within the  $30 \pm 7$  days period.

Deaths, SAEs, and AEs leading to discontinuation of study treatment will be listed separately and, if appropriate, summarized by primary system organ class and preferred term.

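### The glossary ties the fellow treated eye to RVO treatment only, although ranibizumab is also allowed in that eye for other indications, so such an eye is missed by four safety outputs

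*Protocol*

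**What the plan says.** Three parts of the protocol bear on this.

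**The definitions.** The glossary states: "The fellow treated eye is the non-study eye treated with ranibizumab for visual impairment due to macular edema secondary to retinal vein occlusion". Its entry for the fellow untreated eye opens with "The fellow eye that has not been treated with ranibizumab" and continues: "The fellow untreated eye is the non-study eye until treated with ranibizumab for visual impairment due to macular edema secondary to retinal vein occlusion". In Section 4.1, after a sentence on RVO in the fellow eye, the text adds: "The fellow eye treated with ranibizumab is then labeled the fellow treated eye". The notes to Table 6-1 repeat that labelling sentence in the same setting.

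**The permitted treatment.** Section 5.5.4.3 says: "Treatment with ranibizumab for non-RVO indications in the fellow eye will be permitted in the same rule with RVO in the fellow eye". It ties this to what the Japanese package insert allows. At entry, exclusion criterion 23 in Section 4.2 rules out "anticipated treatment in the fellow eye for non-RVO indications during the study". It therefore removes cases foreseen at entry, not those that arise later.

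**The outputs.** Section 9.3.2 summarizes "The number of patients who received 3 or more injections of ranibizumab (study and fellow treated eye) within a" window of about one month. One of the listings in Section 9.5.2.1 is "Any treatment-emergent AEs of the fellow treated eye starting on or after the first treatment with ranibizumab within this eye". Sections 9.3.1 (exposure) and 9.5.2.4 (ocular assessments including IOP) also use the term fellow treated eye.

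**The concern.** Exposure to ranibizumab does not depend on the indication for which the eye was injected. The label that decides which fellow eyes enter the exposure and safety outputs does depend on it. A patient who develops another labelled indication in the fellow eye during the study, and is treated for it, has an injected eye that the glossary does not call treated.

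What is at stake is the completeness of the fellow-eye and two-eye safety reporting. A programmer who follows the glossary would omit that eye's injections from the combined exposure and bilateral counts, and would omit its post-injection ocular events from the listing meant to hold such events. The efficacy comparison is not at stake, because the primary variable counts ranibizumab injections as study treatment and the secondary efficacy endpoints are stated for the study eye.

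**Working it through.** No figure in the protocol rests on this definition, so the check is logical: apply the glossary to each possible fellow eye, then trace the result through each output.

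**Step 1. Classify the fellow eye.** Rule A is the opening sentence of the untreated-eye entry (no ranibizumab at all). Rule B is its next sentence (untreated until given ranibizumab for RVO).

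| Ranibizumab in fellow eye | Treated? | Untreated, rule A? | Untreated, rule B? |
|---|---|---|---|
| None | no | yes | yes |
| For RVO | yes | no | no |
| For a non-RVO indication | no | no | yes |

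The first two rows are consistent. In the third, the eye is not treated under either rule. By rule A it is not untreated either, so it has no label; by rule B it is untreated despite having been injected. The entry therefore contradicts itself for exactly the case that Section 5.5.4.3 allows.

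**Step 2. Trace the third row through the outputs.**

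| Output | Term used | Non-RVO injected eye included? |
|---|---|---|
| 9.3.1 combined exposure summary | fellow treated eye | no |
| 9.3.2 bilateral count | fellow treated eye | no |
| 9.5.2.1 fellow-treated-eye listing | fellow treated eye | no |
| 9.5.2.4 ocular and IOP summary | fellow treated eye | no |
| 9.5.2.1 main treatment-emergent listing | all, except fellow untreated eye after its first ranibizumab treatment | rule A: yes; rule B: no, for post-injection ocular events |
| 9.5.2.1 bilateral-patient listing | injections of study drug | not decided by the label |
| 9.5.2.1 adverse event tables by site | fellow eye | yes |
| 9.5.2.1 by-patient listing of all events | all events, with the eye | yes |
| 9.5.2.1 deaths, SAEs, events leading to discontinuation | all such events | yes |

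**Step 3. The exception in the main listing.** Its evident purpose is to move the events of a newly injected fellow eye to the separate fellow-treated-eye listing. Under rule B, the non-RVO eye is still called untreated after its injection, so the exception removes its post-injection ocular events. The separate listing does not receive them, because the eye is not called treated. They appear in neither of the two listings.

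**Step 4. How many patients.** The protocol gives no rate or count for non-RVO treatment of the fellow eye. Criterion 23 leaves only cases not anticipated at entry. With a target of at least 56 randomized patients, and 59 randomized by 21 January 2018 according to Amendment 2, the number is likely to be small.

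**The case against.** The best defence is that the protocol also supports a reading in which any ranibizumab makes the eye treated. The labelling sentence in Section 4.1 and the Table 6-1 notes names no indication. The opening sentence of the untreated-eye entry names none either. Section 5.5.4.3 places non-RVO treatment under the same rule as RVO treatment, and asks that a fellow eye given ranibizumab be examined like the study eye.

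This shows that the intended meaning may well be the broad one. It does not remove the conflict. The labelling sentence follows directly on text about RVO, the phrase in Section 5.5.4.3 governs how treatment may be given, and the glossary, which is where a definition is looked up, states the RVO condition twice.

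Other parts of the defence stand and limit the point:

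- A reader might infer that the eye's adverse events vanish from safety reporting. They do not: the by-site tables use fellow eye without regard to treatment or indication, and the by-patient, death, SAE and discontinuation listings are unaffected.
- A reader might infer that the adverse event listing for bilateral patients fails in the same way. It counts injections of study drug and does not use the label. Whether a fellow-eye injection counts as study drug is a separate question.
- A reader might take the bilateral count to be the only measure of two-eye exposure. Section 9.3.1 also combines the eyes, though with the same label.
- A reader might picture many uncounted injections per patient, given monthly from the start. Criterion 23 makes that unlikely, since only treatment that was not anticipated at entry can arise.
- The 30 ± 7 days used for the bilateral count is a day-counting detail that depends on a convention the protocol does not state. It forms no part of this point.

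**Conclusion.** The point holds in this limited form. The definition of the fellow treated eye contradicts the treatment allowed in Section 5.5.4.3, and the untreated-eye entry contradicts itself. Read literally, four outputs omit a fellow eye injected for a non-RVO indication. Under rule B, its post-injection ocular events are also missing from the main treatment-emergent listing.

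The conclusion rests on two assumptions: that programming follows the glossary as written, and that at least one patient starts such treatment during the study. If no patient does, nothing changes in the results. The documents do not support a claim that data are lost, since Section 5.5.4.3 requires fellow-eye treatment, adverse events and SAEs to be recorded on the eCRF. Nor do they support any effect on the primary analysis or the sample size. This is a small but clear fault in the definition of outputs, worth correcting before database lock.

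**What to change.** 1. In the glossary, define the fellow treated eye as a non-study eye that has received at least one ranibizumab injection during the study, for any indication. The limit to the study period matters because, for the fellow eye, criterion 23 looks back only 3 months before Baseline, so older injections are possible.
2. Define the fellow untreated eye as the exact complement, and delete the RVO condition from its second sentence. If only the first entry is changed, the same eye would be both treated and, by rule B, untreated.
3. Align the labelling sentences in Section 4.1 and the notes to Table 6-1.
4. Reword the exception in the Section 9.5.2.1 main listing so that post-injection ocular events of any ranibizumab-treated fellow eye go to the fellow-treated-eye listing.

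Sections 9.3.1, 9.3.2 and 9.5.2.4 then need no change, as they take the corrected term. The cost is wording alone: the treatment and event records are already captured, and no treatment rule changes. The only visible effect is that a few more eyes may enter the fellow-treated-eye outputs and a few more patients may count as bilateral.

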## **Amendment 2**

### **Amendment rationale**

The purpose of this amendment is to allow temporary use of phenothiazines for common cold and upper respiratory infection as mentioned in the below section.

Study CRFB002EJP09 was initiated on 15-Dec-2016 and enrollment is currently ongoing. As of 21-Jan-2018, 59 patients have been randomized in the study. This amendment will not impact the study population, drug administration, objectives, endpoints, or study results.

### **Changes to the protocol**

Phenothiazine was included as prohibited medication in the final study protocol, as this medication is known to be toxic to the lens, retina or optic nerve. However, the symptoms are generally thought to occur with long-term use. Therefore, it is reasonable to allow the temporary use of phenothiazine with common cold and upper respiratory infection, which has been clarified in this amended version.

Changes to specific sections of the protocol are shown in the track changes version of the protocol using red underlined for insertions. Appropriate changes are made in [Section 4.2](#), [Section 5.5.8](#), and [Table 5-1](#).

A copy of this amended protocol will be used for Institutional Review Board (IRBs)/Independent Ethics Committee (IECs) submissions.

The health Authority (HA) submission/notification will be assessed by Post-marketing Study Protocol Evaluation Committee (PSPEC) considering local HA requirements.

The changes herein do not affect the trial specific model ICF.

## **Amendment 1**

### **Amendment rationale**

The purpose of this amendment is to update and revise clinical chemistry parameters as mentioned in the below section.

This study is in the start-up phase and not enrolled/screened any patients at the time of this amendment. This amendment will not impact the study population, drug administration, objectives, endpoints, or study results.

### **Changes to the protocol**

The clinical chemistry parameters VEGF-A, VEGF-B, and PlGF are replaced with VEGF in [Table 6-1](#) footnote (# b) and [Section 6.5.4.2](#).

Changes to specific sections of the protocol are shown in the track changes version of the protocol using strike through red font for deletions and red underlined for insertions.

A copy of this amended protocol will be used for Institutional Review Board (IRBs)/Independent Ethics Committee (IECs) submissions.

The health Authority (HA) submission/notification will be assessed by Post-marketing Study Protocol Evaluation Committee (PSPEC) considering local HA requirements.

The changes herein do NOT affect the trial specific model ICF.

## Protocol summary

Protocol number	CRFB002EJP09
Title	A 12-month, phase IV, open-label, randomized, active controlled, 2-arm, multicenter study assessing the efficacy and safety of intravitreal Ranibizumab combined with Grid&Direct short pulse laser photocoagulation versus a PRN Ranibizumab monotherapy in Japanese patients with macular edema secondary to branch retinal vein occlusion (BRVO).
Brief title	Study to show a superior benefit in terms of reduction of ranibizumab injections in patients receiving ranibizumab plus laser photocoagulation combination therapy without loss of efficacy and safety.
Sponsor and Clinical Phase	Novartis Pharma K.K (Phase IV)
Investigation type	Drug, Laser photocoagulation
Study type	Interventional
Purpose and rationale	This study is designed to evaluate comparative efficacy and safety data as well as injection frequency data for ranibizumab using a pro re nata (PRN) dosing, administered with Grid&Direct short pulse laser photocoagulation versus ranibizumab monotherapy using the same dosing up to Month 12 in Japanese patients with visual impairment due to macular edema (ME) secondary to BRVO.
Primary Objective	To demonstrate that PRN regimen (PRN, according to the Japanese label of ranibizumab) of ranibizumab combined with Grid&Direct short pulse laser photocoagulation reduces the burden of frequent ranibizumab injections as compared to ranibizumab monotherapy. The primary objective will be assessed by the difference in the mean number of ranibizumab injections applied up to Month 11 between the 2 treatment arms.
Secondary Objectives	The secondary objectives of this study are as follows: 
 
• To evaluate the efficacy of each arm as assessed by Best-corrected visual acuity (BCVA)
 
• To evaluate the efficacy of each arm as assessed by center subfield thickness (CSFT)
 
• To evaluate the safety of ranibizumab monotherapy and ranibizumab combined with Grid&Direct short pulse laser photocoagulation therapy in Japanese patients as assessed by the type, frequency, and severity of ocular and non-ocular adverse events (AEs) from Baseline (Day 1) to Month 12
 

Study design	This is a Phase IV, randomized, open-label, active-controlled, 2-arm, multicenter study. Patients will be randomized in a 1:1 ratio to 1 of the 2 treatment arms; i.e. Arm 1 ranibizumab monotherapy, Arm 2 ranibizumab with Grid&Direct short pulse laser photocoagulation combination therapy.  In addition to screening and Baseline (Day 1), there will be monthly visits from Month 1 to Month 12.  There will be 3 periods in this study: Screening Period, Treatment Period and Follow-up Period.
Population	This study will include male and female patients (≥20 years old) diagnosed

	
with visual impairment due to ME secondary to BRVO. Assuming an approximate 20% drop out rate, approximately 70 patients will need to be screened to have at least 56 patients found eligible and commencing treatment in the trial.

Key Inclusion criteria
	
Key inclusion criteria:
 
 
• Written informed consent must be obtained before any assessment is performed.
 
• Male or female patients <math>\geq 20</math> years of age.
 
• Diagnosis of visual impairment exclusively due to ME secondary to BRVO.
 
• Best-corrected visual acuity score at Screening and Baseline (Day 1) between 0.5 and 0.05 decimal (i.e., between 73 and 19 letters in Early Treatment Diabetic Retinopathy Study (ETDRS) testing) with Landolt C charts inclusively (i.e., approximate logarithm of the minimum angle of resolution (logMAR) units of 0.3 to 1.30).
 
• At Baseline (Day1), a maximum BCVA gain of 0.2 units logMAR conversion inclusively from screening is allowed as long as the BCVA score does not exceed the upper limit of 0.3 units logMAR.
 
• Increased central subfoveal thickness (<math>> 300 \mu\text{m}</math> at Baseline (Day 1) when measured by SD-OCT).
 
• Duration of vision deterioration <math>\leq 6</math> months (determined by self-report) at screening.
 


Key Exclusion criteria
	
Key exclusion criteria:
 
 
• Pregnant or nursing (lactating) women.
 
• Stroke or myocardial infarction less than 3 months before Screening.
 
• Uncontrolled blood pressure defined as systolic value of <math>>160</math> mm Hg or diastolic value of <math>>100</math> mm Hg at Screening or Baseline (Day 1). Antihypertensive treatment can be initiated and must be taken for at least 30 days after which the patient can be assessed for study eligibility a second time.
 
• Any active periocular or ocular infection or inflammation (e.g., blepharitis, conjunctivitis, keratitis, scleritis, uveitis, endophthalmitis) at the time of Screening or Baseline (Day 1) in either eye.
 
• Uncontrolled glaucoma (intraocular pressure (IOP) <math>\geq 30</math> mm Hg on medication or according to investigator's judgment) at the time of Screening or Baseline (Day 1) or diagnosed within 6 months before Baseline (Day 1) in either eye.
 
• Neovascularization of the iris or neovascular glaucoma in the study eye.
 
• Use of any systemic anti-VEGF drugs within 6 months before Baseline (Day1) (e.g., sorafenib (Nexavar®), sunitinib (Sutent®), bevacizumab (Avastin®), ziv-aflibercept (ZALTRAP®)).
 
• Treatment (or anticipated treatment in the fellow eye for non-RVO indications during the study) with any anti-angiogenic drugs (including any anti-VEGF agents) within 3 months before Baseline (Day1) in fellow eye or before Baseline (Day 1) in the study eye (e.g., pegaptanib (Macugen®), ranibizumab (Lucentis®), bevacizumab (Avastin®), and aflibercept (EYLEA®)).
 
• Panretinal laser photocoagulation within 1 month before Baseline (Day1) or anticipated or scheduled within the next 12 months (Study periods) following Baseline (Day1) in the study eye.
 
• Any giving of focal or grid laser photocoagulation before Baseline
 

	
(Day1) in the study eye.
 
 
• Use of intra- or periocular corticosteroids (including sub-Tenon) within 3 months before Screening in the study eye.
 
• Any use of intraocular corticosteroid implants (e.g., dexamethasone (Ozurdex®), fluocinolone acetonide (Iluvien®)) in the study eye.
 


Study treatment
	
The investigational treatment used in this study is 0.5 mg ranibizumab applied PRN as intravitreal injection of 0.05 mL, with or without Grid&Direct short pulse laser photocoagulation treatment.
 
Arm 1: Patients will start study treatment with ranibizumab on Baseline (Day 1) and having reached stable status (i.e., as per satisfied stabilization criteria as mentioned below) ranibizumab treatment may be temporarily discontinued. Patients should be monitored monthly for visual acuity (VA) and disease activity and ranibizumab injections will be given using PRN regimen. The minimum gap required between 2 injections of ranibizumab will be 30 ± 7 days.
 
Arm 2: Patients will start study treatment with ranibizumab on Baseline (Day 1) and having reached stable status, ranibizumab treatment may be temporarily discontinued. Patients should be monitored monthly for VA and disease activity. Ranibizumab injections are given using PRN regimen. Grid&Direct short pulse laser photocoagulation treatment must be applied to the target within vascular arcades as soon as indicated. Following the complete application of the initial laser treatment, further laser treatment can be applied in the presence of ME due to BRVO at the investigator's discretion at minimal intervals of 30 ± 7 days.
 
PRN (re-treatment/stabilization) criteria:
 
After Baseline (Day 1) visit, if any one or more criteria from the below list is met, the patient should be administrated ranibizumab treatment (re-treatment criteria)
 
 
1. Center subfield thickness ≥ 300 µm
 
2. An increase of CSFT ≥ 20% compare to minimum value during the treatment period.
 
3. The loss of VA due to disease activity secondary to BRVO (disease activity includes ME, intra-retinal cysts, sub-retinal fluid, macular hemorrhage etc.). This criteria is based on Investigator's judgement including the following scenarios: 
 
• The VA is expected to improve if the existing disease activity is removed, hence investigator decides to treat with ranibizumab
 
• The VA is expected to be decreasing because of the existing disease activity, hence investigator decides to treat with ranibizumab
 
• The VA has decreased as compared to the previous month because of the appearance of disease activity, hence investigator decides to treat with ranibizumab (This criterion is to restart ranibizumab after interruption)
 
 
 
 
If all the above criteria are not satisfied, then the patient shouldn't be treated with ranibizumab (stabilization criteria), i.e.,
 
 
• Center subfield thickness < 300 µm
 
• An increase of CSFT < 20% compare to minimum value during the treatment period
 
• Visual acuity is stable and the disease activity is in the state
 


	of not affecting VA (based on investigator's judgement)
Efficacy assessments	Efficacy assessments will include: 

• Decimal and ETDRS Best-Corrected Visual Acuity (BCVA). █ [REDACTED]

• Color fundus photography (CF) [REDACTED] █ [REDACTED]. █ [REDACTED]. █ [REDACTED].

Key safety assessments	Safety assessments will include the following evaluations: AEs, ophthalmic examinations, vital signs, laboratory evaluations, and pregnancy assessments.
Other assessments	No other assessments will be performed.
Data analysis	
The primary variable is the mean number of ranibizumab injections applied up to Month 11 between the 2 treatment arms in patients with visual impairment due to ME secondary to BRVO.
 
The statistical hypothesis testing of the number of ranibizumab treatments will be based on a stratified Cochran-Mantel-Haenszel (CMH) test. Stratification will be done based on categories of baseline decimal VA (<0.3, or ≥ 0.3). Difference of mean number of injections, 95% confidence interval (CI) of difference and one-sided p-value of the CMH test will be reported.
 
No imputation is required for the primary endpoint which is number of ranibizumab injections, based on PRN regimen.

Key words	Macular edema, Branch retinal vein occlusion, best-corrected visual acuity, central subfield thickness, pro re nata, ranibizumab, laser photocoagulation.

